9.1 Recruitment of volunteers

Volunteer recruitment will occur by an advertisement on the University Basel homepage, an occlusion will occur on a "first come. first served" basis.

9.2 Inclusion criteria

- Healthy male volunteers (American Society of Anaesthesiologist's Class I or II)
- Body mass index between 18 and 25kg/m²
- Able to understand the study and the NRS scale
- Able to give informed consent

9.3 Exclusion criteria

- Recreational drug abuse
- Regularly taking medication potentially interfere with pain sensitation (analgesics, antihistamines and calcium and potassium channel blockers)
- Neuropathy
- Chronic pain
- Neuromuscular or psychiatric disease

Inclusion and exclusion criteria will be checked prior to inclusion into the study.

Informed written consent is obtained from every participant after detailed oral and written information by the study stuff.

9.4 Subject Withdrawal

Subjects may withdraw from the study at any time and for any reason (stating reason is not required). If patients elect to do so, data will be anonymized and no further analyses conducted. To replace this study drop-out, an additional patient will be recruited. Drop outs will be reported in the final publication.

The following reasons result in withdrawal:

- AE challenging the health of the subject if continuing the study
- Severe protocol violations
- Administrative troubles

9.5 Expense allowance for participants

Participants will receive a financial compensation for their expenditure of time and possible travel expenses. This compensation is standardized and will be graded with respect to attended interventions.

A one-time financial compensation will be awarded to patients completing the study (250 CHF). The compensation is graduated. Compensation for the first intervention is 100 CHF, for the second 150 CHF. In the event of early termination (before/ during first intervention), patients will be compensated with 20 CHF/h.

10. SAFETY

10.1 Drug studies

During the entire duration of the study, all adverse events (AE) and all serious adverse events (SAEs) are collected, fully investigated and documented in source documents and case report forms (CRF).

Study duration encompassed the time from when the participant signs the informed consent until the last protocol-specific procedure has been completed, including a safety follow-up period.

10.2 Definition and assessment of (serious) adverse events and other safety related events

An AE is any untoward medical occurrence in a patient or a clinical investigation participant administered a pharmaceutical product and which does not necessarily have a causal relationship with the study procedure. An AE can therefore be any unfavourable and unintended sign (including an abnormal laboratory finding), symptom, or disease temporally associated with the use of a medicinal (investigational) product, whether or not related to the medicinal (investigational) product.

[From ICH E2A and E6, "investigational" term only in E6]

A Serious Adverse Event (SAE) is classified as any untoward medical occurrence that:

- results in death
- is life-threatening,
- requires in-patient hospitalization or prolongation of existing hospitalisation,
- results in persistent or significant disability/incapacity, or
- is a congenital anomaly/birth defect.

In addition, important medical events that may not be immediately life-threatening or result in death, or require hospitalisation, but may jeopardise the patient or may require intervention to prevent one of the other outcomes listed above should also usually be considered serious. [ICH E2A]

Examples of such events are intensive treatment in an emergency room or at home for allergic bronchospasm, blood dyscrasias or convulsions that do not result in hospitalisation, or development of drug dependency or drug abuse.

SAEs should be followed until resolution or stabilisation. Participants with ongoing SAEs at study termination (including safety visit) will be further followed up until recovery or until stabilisation of the disease after termination.

10.3 Assessment of Causality

Both Investigator and Sponsor-investigator make a causality assessment of the event to the study drug, based on the criteria listed in the ICH E2A guidelines:

Relationship	Description
Definitely	Temporal relationship
	Improvement after dechallange*
	Recurrence after rechallenge
	(or other proof of drug cause)
Probably	Temporal relationship

	Improvement after dechallenge
	No other cause evident
Possibly	Temporal relationship
	Other cause possible
Unlikely	Any assessable reaction that does not fulfil
	the above conditions
Not related	Causal relationship can be ruled out
*Improvement after dechallenge only taken into consideration, if applicable to reaction	

10.4 Unexpected Adverse Drug Reaction

An "unexpected" adverse drug reaction is an adverse reaction, the nature or severity of which is not consistent with the applicable product information. [ICH E2A]

10.5 Suspected Unexpected Serious Adverse Reactions (SUSARs)

The Sponsor-Investigator evaluates any SAE that has been reported regarding seriousness, causality and expectedness. If the event is related to the investigational product and is both serious and unexpected, it is classified as a SUSAR.

10.6 Assessment of Severity

The Common Terminology Criteria for Adverse Events (CTCAE) Version 4.03 of the National Cancer Institute (published may 2009) are used to classify severity of possible adverse events.

10.7 Reporting of serious adverse events (SAE) and other safety related events

All SAEs will be reported immediately and within a maximum of 24 hours to the Sponsor-Investigator of the study. The Sponsor-Investigator will re-evaluate the SAE and return the form to the site. SAEs resulting in death are reported to the local Ethics Committee (via local Investigator) within 7 days.

10.8 Reporting of SUSARs:

A SUSAR will to be reported to the local Ethics Committee (local event via local Investigator) within 7 days, if the event is fatal, or within 15 days (all other events).

10.9 Reporting of Safety Signals:

All suspected new risks and relevant new aspects of known adverse reactions that require safety related measures, i.e. so called safety signals, must be reported to the Sponsor-Investigator within 24 hours. The Sponsor-Investigator must report the safety signals within 7 days to the local Ethics committee.

10.10 Follow up of (Serious) Adverse Events:

The participant will be told which test substance he had taken to avoid future complications. In case of an acute allergic reaction, the participant is referred to our emergency department

and the study is discontinued. The participant is informed about the applied test substance and will eventually be referred to an allergologist to verify allergic reaction in order to avoid future exposure.

11. Statistical Methods

11.1 Hypothesis

Main hypotheses

We first hypothesize that open label placebo administration leads to a significant reduction in the area under the pain curve (AUPC) from minute 40 to minute 100 compared to no open-label placebo in induced acute pain in healthy male adults (i.e. $B_{1/2}$ vs. A)

Secondary Hypotheses

Secondly, we hypothesize that education and conditioning further reduce the AUPC in the same period of time compared to those patients receiving open-label placebo without education in induced acute pain in healthy male adults (i.e. B_2 vs. B_1).

Finally, we hypothesize that the observed differences in the AUPC will be reflected in both hyperalgesia and allodynia as well as by biomarkers.

11.2 Determination of sample size

Sample size has been determined by a Wilcoxon signed-rank test for the AUPC for Treatments A and B. The AUPC is the product of the NRS x Time. 7 measurements of NRS will be made in total, one every ten minutes. We expect the area under the curve to be 50 NRSxminutes based on a general difference of 1 NRS point and some time for the effect to fully develop. We expect the standard deviations in both groups to be 1 NRS or 60 NRS*min. Using a t-test with a 20% mark-up for non-parametric data we have arrived at a required number of patients of 22. However since 20-30% of participants can be expected to be non-responders to placebo [38] and expecting 10% drop out we have arrived at a total number of patients to be recruited of 32.

11.3 Statistical criteria of termination of the trail:

Upon completion. With such a small sample size, no interim analysis will be conducted.

11.4 Planned Analyses, Datasets, and Analysis Populations:

For the first hypothesis (AUPC for $B_{1/2}$ vs. A) we will conduct a Wilcoxon signed-rank test. Additionally, we conduct a mixed effects model using the AUPC as the dependent outcome and the treatment, the session order (e.g. Treatment B before Treatment A) time during electrical stimulation (in minutes), and finally the individual. This will allow for a more differentiated analysis accounting for temporal and sessional habituation in explaining the treatment effect.

For the effect of education, we will compare the AUPC of: Treatment B_1 vs Treatment B_2 , again by a Wilcoxon signed-rank test.

The outcomes hyperalgesia and allodynia, as well as biomarkers will be examined analogously to the respective comparisons with the AUPC.

11.8 Interim analysis:

Given the small sample size and limited time, no interim analysis will be conducted.

11.9 Safety analysis:

None. However, patients will be under the continuous surveillance of anesthesiology staff.

11.10 Deviation(s) from the original statistical plan:

The statistical plan will be published prior to commencement on clinicaltrials.gov. Any deviations from the statistical plan will be reported and justified in the final report.

11.11 Handling of missing data and drop outs:

All available data will be used, as far as possible considering the paired nature most of the tests. As long as the participant completes both treatments and data is complete for the primary analysis, the data will count as sufficiently complete. Participants electing to drop-out of the study will be replaced by another participant. However, whatever data is available at the time of drop-out will be analysed. Data completeness will be reported in the final publication and a consort diagram will be made. If a participant withdraws his agreement from the study all obtained data will be immediately deleted. Only anonymized data will be used for publication. Obtained cortisol probes will be destroyed after analyzation and will not be used for further research.

12. Quality Assurance and Control

12.1 Data handling and record keeping / archiving:

Personal data is kept in a computer database, and all CRFs and informed consents are kept in a folder and archived for a minimum of 10 years.

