Study duration:	The duration of the study from the first participant in to the last participant out is 14 weeks. Duration of an individual participant: minimum 2 weeks (time from primary assessment with 1 st intervention until 2 nd intervention).		
Study Schedule:	First inclusion: December 2017 Last intervention in April 2018.		
Investigator(s):	[name] Senior Physician Department of Anaesthesiology University of Basel (USB) [name] [name] CH [contact] [contact] E-mail: [contact]		

	[name], MSc
	Research Fellow,
	Department of Anaesthesiology University of Basel (USB)
	[name]
	[name] CH
	[contact]
	[contact]
	E-mail: [contact]
	[name], PD
	Senior Physician
	Department of Anaesthesiology University of Basel (USB)
	[name]
	[name] CH
	[contact]
	[contact]
	E-mail: [contact]
	[name]
	Scientific assistant, doctoral candidate
	Department of Anaesthesiology University of Basel (USB)
	[name]
	[name] CH
	[contact]
	[contact]
	E-mail: [contact]
	[name], Prof.
	[name]
	[name]
	[contact]
	[contact]
	E-mail: [contact]
	[name], PD
	Head of the Pain Unit
	Department of Anaesthesiology University of Basel (USB)
	[name]
	[name] CH
	[contact]
	[contact]
	E-mail: [contact]
Study Center(s):	Monocentric study: Basel University Hospital
Statistical	We will conduct a number of analyses as delineated in the statistics
Considerations:	section. Briefly put, for each of the hypotheses a simpler, generally
	1
	paired nonparametric test will be conducted. Additionally, a mixed-
	effects model will be employed to attain further information and account
	for the order of treatments, and the effect of time.
GCP Statement:	This study will be conducted in compliance with the protocol, the
	current version of the Declaration of Helsinki, the ICH-G, as well as all
1	, , , , , , , , , , , , , , , , , , , ,

national legal und regulatory requirements.

Study summary in local language:

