5.2 Secondary outcomes

- The pain response measured by the AUPC (NRS every 10 minutes during electrical stimulation) will be used for further comparison of the two different treatment interventions every participant recieves during the study. We compare the participants received a education about placebo to the non prior educated participants.
- 2. Hyperalgesia and allodynia will be measured analogously to the NRS as above.
- 3. Saliva concentration of cortisol, measured at baseline, 30, 60 and 100 minutes after pain induction.

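### The supplementary mixed model in 11.4 pairs AUPC, which has one value per session, with a minutes term that cannot be estimated

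*Combined protocol and SAP*

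**What the plan says.** Section 11.4 tests the first hypothesis with a Wilcoxon signed-rank test and adds "a mixed effects model using the AUPC as the dependent outcome and the treatment, the session order". The remaining terms are "time during electrical stimulation (in minutes), and finally the individual". The order term is explained as "the session order (e.g. Treatment B before Treatment A)". The model is said to allow a more differentiated analysis, "accounting for temporal and sessional habituation in explaining the treatment effect". No term is labelled fixed or random, and no covariance structure is given.

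The outcome is defined elsewhere. Section 11.1 speaks of the "area under the pain curve (AUPC) from minute 40 to minute 100", and 5.1 gives the same window. The synopsis starts the window at minute 30, which differs but is also fixed. Section 11.2 states that "7 measurements of NRS will be made in total, one every ten minutes" and describes AUPC as NRS multiplied by time. Section 5.2 glosses AUPC as "NRS every 10 minutes during electrical stimulation". The synopsis says the mixed model is there to account "for the order of treatments, and the effect of time".

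**The concern.** An area over a fixed window has already summed over time, so it cannot also vary with minutes. A model with that area as its outcome cannot carry a minutes effect, yet 11.4 relies on that effect for its claim about temporal habituation. This is a stated rule that fails, not a missing detail.

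The order term has a related difficulty. Which treatment came first is a fixed attribute of a participant. A change from session 1 to session 2 happens within a participant, and a term that is constant within a participant cannot adjust for it.

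What is at stake is a stated property of a supplementary analysis, and the freedom to choose the repair late. More than one repair is possible, and one natural version gives a treatment standard error that is too small if sessions vary.

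**Working it through.** **Inputs from the documents.** Window: minutes 40 to 100 (5.1, 11.1). Readings: one every 10 minutes, 7 per session (11.2). Sessions: 2 per participant (7.2). Participants: 32 (7.1). SD of AUPC in each condition: 60 NRS×min (11.2).

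**Assumed, because the documents give no value.** Correlation between sessions 0.5; session effects of 15, 30 or 60 NRS×min; session share s of the within-participant variance.

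**The plan's own figures.** (100 − 40)/10 + 1 = 7 readings, as stated. The 22 participants can also be reproduced: a paired t-test for a difference of 50 with SD of the difference 60×√(2×(1 − 0.5)) = 60, assuming two-sided 5% and 90% power, needs 18, and 18×1.2 = 21.6, rounded up to 22. The mixed model plays no part in that calculation.

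**1. Is the minutes effect estimable?** With AUPC as outcome there are 32×2 = 64 rows. Minutes is the same in each row, so its column is a multiple of the intercept. The matrix (intercept, treatment, order, minutes) has rank 3 of 4; without minutes it has rank 3 of 3. The result with minutes is the same for 22, 29 or 32 participants and for order coded as sequence or as session number. With the NRS readings as outcome there are 32×2×7 = 448 rows and the rank is 4 of 4. No variance assumption enters.

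Copying each AUPC onto seven time rows is no cure. In simulation (assumed SDs 0.7 participant, 0.7 session, 0.5 residual NRS; 300 runs) the time coefficient was zero to rounding, the treatment standard error fell from 10.8 to 3.0 NRS×min, and false rejection rose from about 6% to about 62%.

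**2. Sequence or session number.** Let D be AUPC under B minus AUPC under A, and p the session effect. D shifts by +p or −p according to sequence.
- With session number in the model, SE = 60/√32 = 10.6.
- With sequence only and a 16/16 split, p stays in the error: SE = √((60² + p²)/32). For p = 15, 30, 60 this is 10.9, 11.9, 15.0.
- Simulation gave 10.5 for session number, and 10.8, 11.8 and 15.0 for sequence.
- With 16/16 the shifts cancel, so there is no bias. With an assumed 18/14 split the estimate moves by p×(18 − 14)/32 = 1.9, 3.75 or 7.5 NRS×min.

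**3. Repeated NRS with a participant effect only.** Scale the within-participant variance to 1, with s between sessions and 1 − s residual. The true variance of one participant's difference in session means is 2[s + (1 − s)/7] = (2/7)(1 + 6s). Each participant has 14 readings and 13 within-participant degrees of freedom, one of them between sessions. The model's residual mean square is therefore on average (1 − s) + 7s/13 = 1 − 6s/13, and it credits (2/7)(1 − 6s/13). The ratio of reported to true standard error is √[(1 − 6s/13)/(1 + 6s)], and the type I error is about 2Φ(−1.96 × ratio).

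| s (assumed) | SE ratio | Type I error, formula | Simulated, N = 32 |
|---|---|---|---|
| 0 | 1.00 | 5% | 4.8% |
| 10% | 0.77 | 13% | 13.3% |
| 20% | 0.64 | 21% | 21.2% |
| 50% | 0.44 | 39% | 39.2% |
| 80% | 0.33 | 52% | 52.3% |

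Adding a participant-by-session effect gave 4.7% to 5.3%.

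**4. What the minutes term does for the treatment comparison.** With AUPC, treatment and session number, and minutes dropped, rejection under the null was 4.8% to 5.3%. With complete NRS data and both random effects, an additive minutes term changes nothing: in six simulated data sets the treatment estimate and standard error agreed to four decimals with and without it, for example −0.1461 (SE 0.1543).

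**The case against.** The best defence is that AUPC in 11.4 is loose shorthand for the NRS series. The 11.2 description, the gloss in 5.2 and the synopsis reference to time all point that way, and the minutes effect is then estimable. This reading is plausible. But no section names the NRS readings as this model's outcome, and 11.4 names AUPC. Nor does the reading complete the plan: the individual is then the only clustering unit listed, and whether sessions get their own effect is left open. Variation between sessions is credible, because the current is recalibrated in each session (7.7) and the sessions are at least two weeks apart (synopsis).

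Second, the sequence wording is only an example in parentheses, and the next sentence states the aim as sessional habituation, so a session-position term may be intended. That stands. The sequence problem belongs to the literal reading, and the sizes in step 2 rest on assumed values.

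Third, 11.10 says the statistical plan is published before commencement and that deviations are reported and justified. A reader might infer that the repair will be picked after looking at the data. The documents do not say so; 7.11 opens the randomisation only after the last session, so the wording can be settled before then. What remains is that it could be chosen late, and that reporting a deviation discloses a choice without pre-specifying it.

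**Conclusion.** Wrong as written; minor. That minutes is not estimable with AUPC as outcome follows from the definition of AUPC alone. The model therefore cannot account for temporal habituation as 11.4 claims. The literal order term cannot adjust for a session 1 to session 2 change, at a cost in precision when order is balanced.

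Two stronger readings are not supported. A reader might infer that the trial's main result is at risk. It is not: the primary Wilcoxon test and the sample size do not use this model, and within-session habituation does not bias the treatment comparison, because measurement is identical in both sessions (7.8), order is randomised (7.2) and condition A serves as the habituation control (synopsis). A reader might also take type I errors of 13% to 52% as the size of the error in the plan. They describe one possible repair that the plan does not specify, under assumed session shares, and serve only as a caution about that repair.

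**What to change.** State in 11.4 which model is meant:

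- **(a)** AUPC as outcome, one row per session, with treatment, session number (1 or 2) and a random participant effect. Delete the minutes term and the word temporal from the habituation sentence.
- **(b)** The seven NRS readings as outcome, with treatment, session number, minutes, and random participant plus participant-by-session effects.

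In either case make clear that the order term is session number, since that is what captures habituation between sessions.

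The cost is wording only, with no new data. Option (a) gives up the claim about temporal habituation. Option (b) keeps it but may give a wider treatment standard error than a participant effect alone. Record the change and its reason before unblinding, as 11.10 requires deviations to be reported and justified.

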7.2 General study design and justification of design

An assessor-blinded, randomized crossover study design will be applied. Each patient will undergo each of the two treatments (A-B) listed below. Furthermore, patients will be randomized to either receive placebo education or to not receive placebo education (e.g. B_1 = placebo education; B_2 = no placebo education). In other words, each patient will receive one of the two following treatment sets: either (A, B_1) or (A, B_2); the individual components of these sets will be randomized.

TREATMENT	General (visible)	Open drug application	
A→ No treatment	Infusion RL	No	
intervention	Infusion rate: 100ml/h		

B _{1,2} →Open-label	Infusion RL	OLP
Placebo alone	Infusion rate: 100ml/h	

Table 1: Overview study interventions

In each treatment the patient will receive a standard infusion containing only Ringer lactate (RL) infused at a rate of 100ml/h. The purpose of this infusion is simply to keep venous access.

To avoid any systematic bias the assignment of the study groups will be performed in a balanced randomized manner. To control for excitement and habituation effects we operate the interventions in a randomized order in every participant.

The participants are recruited by an advertisement on the University of Basel homepage and eligible volunteers will be included on a "first come, first served" basis.

Study participants are orally and written informed about study aims and interventions before the first assessment.

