7.7 General setup of intradermal electrical stimulation (cp. Figure 3)

Two microdialysis catheters with internal stainless steel wires are inserted in parallel into the intradermal, volar surface of the contralateral forearm for a length of approximately 10mm and are separated 5mm from each other. The catheters are filled with 0.9% saline and a continuous flow of 0.2µl/min ensured by a syringe pump (Perfusor®) to facilitate conduction. The stainless steel wires are attached to a constant current stimulator (manufactured by [name] et al.) and monophasic, rectangular electrical pulses of 0.5ms duration are applied with alternating polarity at 2 Hz. The current will be increased to target a pain rating of 6 of 10 on a numeric rating scale (NRS) (0= no pain and 10 maximum tolerable pain). Three further increases in current will be made every 5 min for the next 15min to compensate for habituation. This final current will be kept constant until the end of the particular experiment (100min cp. figure 4). After calibration to NRS 6 there is no further increase of the current.

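### The mixed model's order term reads as treatment sequence, which cannot adjust for habituation between sessions; define it as session number (1 or 2)

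*Combined protocol and SAP*

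**What the plan says.** For the first hypothesis (open-label placebo against no treatment on the AUPC), section 11.4 states that "we will conduct a Wilcoxon signed-rank test. Additionally, we conduct a mixed effects model". The model takes the AUPC as outcome. It lists treatment, "the session order (e.g. Treatment B before Treatment A"), time during stimulation and the individual. Its stated purpose is "accounting for temporal and sessional habituation in explaining the treatment effect". The synopsis, under Statistical Considerations, says the same model accounts "for the order of treatments, and the effect of time".

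Neither place gives a coding, a first-or-second-session term, or a treatment-by-order interaction.

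Two design features bear on the point. Section 7.2 says "To control for excitement and habituation effects we operate the interventions in a randomized order in every participant", and section 7.7 says "The current will be increased to target a pain rating of 6 of 10 on a numeric rating scale (NRS"), which is done in each experiment. Section 11.2 is written for the unadjusted test: "Sample size has been determined by a Wilcoxon signed-rank test for the AUPC for Treatments A and B".

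**The concern.** The example in 11.4 and the synopsis wording both describe sequence: A-then-B or B-then-A. Each participant has one sequence, so it takes the same value in both of his sessions. A change from the first to the second session happens within a participant, so a main effect of sequence cannot pick it up. Only session number (1 or 2) can.

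The signed-rank test has no session term either. If the model is coded as its example reads, the planned analyses of the primary comparison contain no session adjustment, yet the report would claim one. The sponsor takes habituation seriously: section 7.6 omits a training session partly because of it, and session 1 is itself an exposure before session 2.

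At stake are the precision of the estimate and, if the two sequences end up unequal in size, its location. Section 11.4 analyses hyperalgesia, allodynia and biomarkers in the same way, so the ambiguity may carry over to outcomes that the titration to NRS 6 does not target.

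**Working it through.** **Inputs from section 11.2.** Effect 50 NRS x min, SD 60 per treatment, 22 participants required, 32 recruited, 20-30% non-responders, 10% drop-out. Power, alpha, sidedness and the SD of the paired difference are not stated.

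**Reproducing the plan's figure.** A paired t-test with effect 50, SD of the difference 60 (within-person correlation 0.5), two-sided 5% and 90% power needs 18. Then 18 x 1.2 = 21.6, rounded up to 22; 22/0.75 = 29.3, or 22 x 1.3 = 28.6, giving about 29; 29 x 1.1 = 31.9, giving 32. The 22 also follows from 80% power with correlation 0.3, so the SD of the difference is not fixed by the text. I use 60, and 85 (60 x √2) for uncorrelated sessions.

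**Assumptions.** A session-2 shift of 15, 30 or 60 NRS x min; the documents give none. A shift of 60 exceeds the planned effect of 50 and serves as an upper bound. With 75% responders at 50 and 25% at 0, the mean effect is 0.75 x 50 = 37.5.

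**Algebra.** Let τ be the B minus A effect and π the shift from session 1 to 2. B minus A has mean τ + π in A-then-B participants and τ - π in B-then-A participants. A sequence effect adds equally to both sessions and cancels.

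- No order term, or sequence: the estimate has mean τ + π(nAB - nBA)/N. At equal sequences its SE is about √(σ² + π²)/√N.
- Session number: the estimate averages the two sequence means, so its mean is τ. At equal sequences its SE is about σ/√N.

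With σ = 60, π = -30 and 16:16, √(3600 + 900)/√32 = 11.9 and 60/√32 = 10.6.

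**Fitted mixed models** (AUPC, random intercept, REML, 300 data sets per split, effect -37.5, shift -30):

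| Split | No order term | Sequence | Session number |
|---|---|---|---|
| 16:16 | -37.94 (SE 11.80) | -37.94 (SE 11.81) | -37.94 (SE 10.55) |
| 18:14 | -41.62 (SE 11.71) | -41.62 (SE 11.71) | -37.92 (SE 10.56) |

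Estimates with and without sequence agreed to within 1e-12 in all 600 data sets. At 16:16 session number cuts the SE by 1 - 10.55/11.81 = 11%.

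**Movement of the estimate**, shift x (nAB - nBA)/N, for shifts 15/30/60: at 17:15 (2/32) 0.9/1.9/3.8; at 18:14 (4/32) 1.9/3.8/7.5.

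**Power** (two-sided 5%, exact critical values, 40,000 runs per cell, 75% responders). The period-adjusted test is a rank-sum test on session 2 minus session 1, compared between sequences.

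| SD, split | Signed-rank at shift 0/15/30/60 | Period-adjusted |
|---|---|---|
| 60, 16:16 | 88/87/83/64% | 87% |
| 60, 15:14 | 84/84/81/64% | 83-84% |
| 85, 16:16 | 63/62/58/45% | 61-62% |

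If the SD of 60 already contains a shift of 30, the residual SD is √(3600 - 900) = 52.0, and power at 16:16 is 90.6% against 94.0%.

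**Type I error of the signed-rank test** (SD 60, same shifts): 16:16 4.8/4.4/2.8/0.6%; 18:14 4.8/4.5/3.7/1.8%; 19:13 5.0/5.1/5.3/4.1%. The rank-sum test stays at 4.5-5.1%. Only a strong imbalance makes the signed-rank test liberal: at 20:12 it gives about 7% at a shift of 30 and 8% at 60 (4,000 runs).

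**The case against.** The term is called session order, the bracket is only an example, and the next sentence gives the purpose as habituation between sessions. An analyst could well code session number. This is fair: the text shows an unspecified coding, not a mis-coded model. But the only example given, and the synopsis, both point to sequence, and coding the model that way removes its stated property.

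The model is supplementary, and the primary test is valid. This stands. At equal sequences the estimate is also unbiased under either coding, so the gain there is precision only.

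The shift is unknown, and the design works against a large one: order is randomised, the current is titrated afresh, and sessions are at least two weeks apart. A shift of 60 means a full NRS point throughout minutes 40 to 100. This stands too; the large power loss belongs to the upper bound alone.

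Unequal sequences are an assumption. Section 7.2 promises balance for the study groups without saying whether this covers sequence, and sections 9.4 and 11.11 replace drop-outs without saying that the replacement takes the same sequence. Imbalance is possible, not shown.

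The fitted models omit the listed time term. A check on seven NRS ratings per session (one data set, 18:14) gave -0.5092 with and without sequence and -0.4293 with session number. The algebra carries over, but the quoted SE gains are shown only for the AUPC model.

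Finally, once session number is in the mixed model, that model is already a period-adjusted analysis. A rank-sum version matches the primary test more closely but is largely redundant.

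**Conclusion.** The point holds. Coded as its example reads, the mixed model does not account for habituation between sessions, and nothing else planned for the primary comparison does.

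The consequence is moderate. For an assumed shift of 30 and SD of the difference of 60, the SE is about 11% larger than it need be, signed-rank power is about 4 points lower at 16:16, and the estimate moves by about 3.8 NRS x min at 18:14. At a shift of 15 or below there is no power gain; at the upper bound of 60 the gap is 23 points. These sizes depend on the assumed shift, SD and split. That a sequence main effect cannot adjust for session depends on none of them; it needs only complete pairs. This is a matter of a correctly adjusted and tighter estimate, not the repair of an invalid test.

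**What to change.** 1. In 11.4, define the mixed-model term as session number (1 or 2), with sequence as an optional extra, and align the phrase in the synopsis.
2. Keep the signed-rank test as primary. As a supporting analysis of the same comparison, pre-specify a Wilcoxon rank-sum test on session 2 minus session 1 AUPC, A-then-B against B-then-A. This is of lower priority than item 1.

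The cost is one definition, one phrase and, for item 2, one supporting analysis. The primary test and the sample size do not change. With no session effect, session coding costs nothing measurable in SE at 16:16 (10.5 either way) and about 0.8% at 18:14. Making the period-adjusted test primary is optional. It would cost about 1 point of power with no session effect (88.4% to 87.4% at 16:16) and require changes to 11.2 and to the plan published under 11.10. Since 11.10 requires deviations to be justified, the wording is best settled before the study starts.
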